14.2. Withdrawal from Study

Participants who sign the informed consent form, and are randomized and subsequently withdraw, or are withdrawn or discontinued from the study, will not be replaced.

Participants are free to withdraw from participation in the study at any time upon request. They will be documented as: "withdrawn by participant" or "withdrawn by study PI". Data collected until the point of withdrawal can still be included in analysis, using the intention-to-treat (ITT) approach.

Participant withdrawal will be documented as a Protocol Event and reason will be documented as a NOTE TO FILE form.

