9.2. Medical record review

“Baseline pregnancy” weight will be defined as the earliest measured weight in prenatal care obtained from prenatal medical records. We will also abstract height, blood pressure and comorbid conditions from medical records. Participants will consent to prenatal and infant medical record release during the consent process. [Most of our participants will not be Johns Hopkins patients. For the few participants who are Johns Hopkins patients, following consent to review medical records, the study team will access medical records via the Epic for manual data extraction of height, weight, and comorbid conditions. We will not be submitting a CCDA request. For all non Johns Hopkins patients, we will be requesting their medical records directly from their prenatal care provider via secure fax or secure email.](#)

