9.2. Assessment of maternal weight using the Home Scale

Maternal weights (measured at 37-weeks, 2 months, 4 months, and 6 months postpartum) will be measured in light indoor clothes without shoes and recorded by a home **study scale** (BodyTrace or a similar product) and recorded and transmitted to the study team automatically using cellular connectivity (no WIFI or cellular plan required). The scale will be delivered to the participant's home upon enrollment. The cellular enabled scales provide valid weight measures and have been used by several large-scale weight interventions⁶⁹.

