9.3.11. Satisfaction Survey with the H42-HV Intervention Components

We will assess satisfaction with Health Coaching, Mobile Phone tracking, web-based platform by participants and providers at study completion using a survey tool our team has designed and tested.

9.4. Medicaid claims data. We will request and obtain a data extract of Maryland Medicaid data for all consented participants to assess maternal and infant healthcare utilization outcomes (i.e., attendance at prenatal care visits, postpartum OBGYN visit, primary care visits, infant visits, receipt of infant vaccines). We will have a data use agreement with the Maryland department of health.

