14.0 DISCONTINUATION AND WITHDRAWAL OF PARTICIPANTS

Participants who discontinue the study early will be asked to complete remaining assessments at the time of discontinuation, if feasible and acceptable to the participant. All reasons for discontinuation will be documented clearly in study records

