14.1. Discontinuation of study

An investigator may discontinue a participant from the study for the following reasons:

- Home visiting program staff, study investigators or Study Safety Officer does not think participation is in the participant's best interest or might be harmful;
- Significant study intervention non-compliance or disruptive behavior (e.g., argumentative with study staff or coach);
- Study is stopped;
- There may be other reasons to that we do not know at this time.

For pregnant women who experience a stillborn or intrauterine fetal demise, we will assess whether she would like to continue in the program, transitioning to the postpartum phase of data collection and/or intervention. Participants will not be discontinued if they choose to have baby adopted.

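### The discontinuation rules do not separate stopping coaching from leaving the study, so 6-month weights and utilisation data may be lost from women who have not revoked consent

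*Combined protocol and SAP*

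**What the plan says.** Section 14.0 (Discontinuation and Withdrawal of Participants) opens with: "Participants who discontinue the study early will be asked to complete remaining assessments at the time of discontinuation, if feasible and acceptable to the participant".

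Section 14.1 (Discontinuation of study) lists the grounds on which an investigator may discontinue a woman. One is "Significant study intervention non-compliance or disruptive behavior (e.g., argumentative with study staff or coach". For stillbirth or fetal demise, the same section lets the woman choose whether to go on with postpartum data collection, the intervention, or both.

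Section 14.2 (Withdrawal from Study) groups the routes out: women who "are randomized and subsequently withdraw, or are withdrawn or discontinued from the study, will not be replaced". Two labels are recorded, and they show whether the woman or the PI took the decision. On data, the section says: "Data collected until the point of withdrawal can still be included in analysis, using the intention-to-treat (ITT) approach".

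Three data sources bear on this:
- Section 9.4 (Medicaid claims data): "We will request and obtain a data extract of Maryland Medicaid data for all consented participants".
- Section 9.2 (Medical record review): "Participants will consent to prenatal and infant medical record release during the consent process".
- Section 9.2 (Assessment of maternal weight using the Home Scale): weights are "recorded and transmitted to the study team automatically using cellular connectivity".

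**The concern.** A woman can stop coaching, stop being contacted, or refuse further use of her data. These are different events, and only the last requires her outcomes to be missing. Apart from the fetal-loss case, the plan does not distinguish them. Its labels record who decided, not what stops.

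The weak spot is investigator discontinuation for non-compliance with the intervention. Such a woman may have revoked nothing. Only one arm receives coaching, so this ground can arise mainly there. If follow-up ends with it, outcomes go missing for a reason linked to adherence, and mostly on one side of the comparison.

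Two sets of outcomes are at stake. The first is the primary one, weight retention at 6 months. The second is utilisation, which Section 15.3 models as a binary indicator of conforming to recommended care. If claims stop at withdrawal and nothing marks the later period as unobserved, visits that were not captured could be counted as not made.

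**Working it through.** **1. The plan's own figures.** Section 16.0 gives 360 randomized, 30% loss, two-sided alpha 0.05 and 90% power.

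- Effective number: 360 × 0.70 = 252, or 126 per arm. Planned loss: 360 − 252 = 108.
- Normal approximation: MDD = (1.960 + 1.282) × SD × √(2/126). For SD 5.5, 7.0, 8.0 and 8.8 kg this gives 2.25, 2.86, 3.27 and 3.59 kg.
- Two-sample t-test (noncentral t, 250 df): 2.255, 2.870, 3.280 and 3.608 kg, against 2.26, 2.87, 3.28 and 3.61 kg in Table 6.

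Table 6 reproduces. It already absorbs 108 missing 6-month weights from all causes, so the withdrawal wording makes no stated figure wrong.

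**2. Assessment at exit against the primary endpoint.** Section 14.1 (Primary Outcome) defines the endpoint by the study-scale weight at 6 months after delivery. Section 14.0 asks for outstanding assessments when the woman leaves. The model in Section 15.2 has baseline and visits at 2, 4 and 6 months postpartum. A weight taken at exit during pregnancy fits none of these visits, and one taken at 2 months is not the 6-month value. The exit assessment therefore does not replace the endpoint.

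**3. Missing at random.** The mixed model includes arm, visit, the stratification factors and all available weights. A different loss rate by arm does not by itself break the assumption. It fails if, given arm and the weights already seen, loss still depends on the unseen 6-month weight. Discontinuation for non-compliance is a plausible route: adherence is not in the model, and it may predict later weight. Continuing to measure these women removes the problem for those who agree.

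**4. Claims.** Section 9.4 covers all consented participants and gives no rule for withdrawal. Section 14.2 covers data up to withdrawal and does not mention claims. For a Medicaid recipient who withdraws, an analyst cannot tell from the two sections whether later claims are in or out. Both sentences can be true together, so they are unreconciled rather than contradictory.

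**5. What each source can recover.**
- Claims: utilisation only, and only for Maryland Medicaid enrollees (Sections 8.2 and 15.1).
- Infant records: infant growth only.
- Scale: the primary outcome, but only if the woman weighs herself.

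Claims and infant records alone therefore add 0 women to the 252.

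**The case against.** The best defence is that this is silence, not restriction. The sentence in Section 14.2 permits earlier data to be kept and does not exclude later data. Nothing says that a woman who declines coaching calls has thereby withdrawn, so continued follow-up may already be the default for her. Section 14.0 does seek data at exit, the fetal-loss provision shows that the authors can separate coaching from follow-up, and Sections 15.1 and 15.2 commit to ITT with all randomized women. No text says that claims will be truncated or that absent claims will be coded as no visit, and utilisation also has a survey source in Table 3.

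Most of this stands, and it rules out several stronger readings that a reader might infer:
- That Section 14.2 forbids use of later data. Its wording is permissive; the limit is an inference.
- That Sections 14.2 and 9.4 contradict each other. Section 9.4 is silent on withdrawal.
- That the scale yields the primary outcome without the woman. Only transmission is automatic.
- That data are lost needlessly. This depends on the scope of consent, and the consent pages were not among the documents reviewed.

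The defence does not cover women discontinued by the investigator. Section 14.2 handles them alongside those who withdraw, Section 14.0 seeks their assessments at exit rather than on schedule, and no text says that their 6-month follow-up continues.

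**Conclusion.** The point holds as a gap in the follow-up rules that is worth closing. The plan should say what stops when a woman is discontinued or withdraws, and which later data are analysed. The argument concerns possible bias related to arm and an undefined rule; it is not about power.

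The size is unknown. A reader might be tempted to convert recovered women into a smaller detectable difference, but the documents give no withdrawal rate. The 30% in Section 16.0 mixes several causes, including censoring for a new pregnancy, and women who simply stop responding are not formal withdrawals. No gain in the MDD can be supported.

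The conclusion rests on two assumptions: that some women are discontinued or withdraw without revoking consent for data, and that staff would take the wording of Sections 14.0 to 14.2 as the end of follow-up. The point does not concern when an investigator should discontinue a woman, only what happens to her follow-up afterwards.

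**What to change.** In Sections 14.0 to 14.2 and on the withdrawal form, record the level that applies:

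- (a) Coaching stops; scheduled assessments continue, including the 6-month weight.
- (b) Contact stops; the woman agrees to continued use of claims, infant records and any scale readings she chooses to send.
- (c) No further data use.

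State that data arising after discontinuation under (a) and (b) enter the ITT analyses. Treat utilisation after a level (c) withdrawal as missing, not as no visit. Bring Section 9.4 and Sections 14.0, 14.1 (Discontinuation of study) and 14.2 into line, and check the levels against the scope of the consent form before adopting them.

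The cost is an IRB amendment, slightly longer forms, and updated forms for women already enrolled. In return, women who stop only the coaching can still contribute the primary outcome. The gain from claims and infant records is confined to secondary outcomes.

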14. DEFINITION OF PRIMARY AND SECONDARY OUTCOMES

14.1. Primary Outcome:

Postpartum weight retention at 6 months after delivery, defined as the difference between baseline weight (\leq 15 week gestation from medical records) and 6 month maternal weight (measured by cellularly enabled study scale) in pounds (lbs).

14.2 Maternal Secondary Outcomes

Gestational Weight Gain (GWG), defined as the difference between weight at 37-weeks postpartum (measured by cellularly enabled study scale) and pre-pregnancy weight (\leq 15 week gestation from medical records). Proportion who gain above the IOM recommended weight⁸⁴ will also be calculated.

14.3 Infant secondary outcomes

Infant growth outcomes of weight, length, and head circumference – at birth, 4 and 6 months – will be self-reported in surveys and will be verified using infant medical records.

14.4. Other outcomes including diet, physical activity, depression, stress, sleep and social support will be self-reported using online surveys created from standard survey instruments^{85,86,87,57,80,81,72}

15. DATA ANALYSIS

15.1 General Approaches

Compare the effectiveness of the H42-HV program using a remotely-delivered health coaching intervention integrated into home visiting with mHIP-HV among 400 pregnant and postpartum women enrolled from early home visiting programs in Maryland:

- Primary outcome: PPWR at 6 months after delivery
- Maternal secondary outcomes: GWG (37 week minus baseline pregnancy [≤ 15 week gestation] weight); Proportion with excessive GWG.
- Infant secondary outcomes: Weight at birth, 2 months, 4 months, and 6 months of age will be gathered as maternal self-report via online surveys and verified with infant medical records.
- Maternal and infant health care utilization, including receipt of postpartum care, ER visits and routine well infant visits, captured for those participants who are Medicaid recipients using claims data.
- Other outcomes: Maternal health behaviors (diet, physical activity, and breastfeeding); Maternal wellness (depression, sleep, and stress)

The main analyses for the primary and secondary outcomes will follow the ITT principle. The analysis for PPWR will utilize a mixed effects model to assess between group difference in mean of total PPWR.

15.2. Main analytic model for the primary outcome of PPWR (difference between pre-pregnancy weight and weight at 6 months postpartum).

We will carry out the main analysis to assess the between group difference using a mixed effects model characterized by a mean model relating the outcome to the predictors and a variance-covariance model addressing variance of all available longitudinal weight outcomes and correlation between outcomes measured overtime within individual. The predictors in the mean model will include a group indicator (0 for Group B and 1 for Group A), 3 visit indicators for 2, 4, and 6 months respectively, with 0 for baseline and 1 for the specific month postpartum the visit indicator corresponding to, and the group by visit interaction terms, adjusting for study sites, BMI category, and gestation at the time of enrollment used for randomization stratification, all as fixed effects. The regression coefficient of the group by 6-months postpartum weight interaction term will estimate the primary outcome, i.e., mean difference in PPWR at 6-months between intervention and control groups. We will use an unstructured variance-covariance model to allow full flexibility on outcome variances and correlations. Data from all participants randomized will be used in this analysis, including missing data which will be included using a software specified missing indicator.

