5.2. Randomized groups

5.2.2 Intervention Group: Healthy for Two -Home Visiting (H42-HV)

Those assigned to the intervention group will receive the 8 to 14 month H42 health coaching intervention in addition to usual home visiting and usual prenatal and postpartum care clinical services. Intervention duration will depend on the participant's gestational age at the of enrollment. Participants can be enrolled as early in pregnancy as 12 weeks gestation and as late as 33 weeks gestation. All participants would be enrolled for 6 months postpartum.

Therefore, the minimum time in the intervention would be 8 months and maximum would be 14 months.

5.2.3 “Usual Home Visiting Plus” Comparison Group (mHIP-HV)

Those assigned to the “usual home visiting plus” comparison group, called maintain health in pregnancy (mHIP-HV), will receive the typical, evidence-based experience in their home visiting program in addition to their usual prenatal and postpartum care clinical services. In addition, we will provide a brief (less than 5 minutes) maternal warning signs educational video that is available in English or Spanish. The video was developed for a home visiting client audience and is publicly available, <https://mdmom.org/warningsigns>.

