Enrollment/ Randomization assignment to H42-HV or mHIP-HV	
 • Once the participant has completed the baseline survey and has registered one weight on the home study scale, research staff will schedule a mutually convenient time for the randomization visit. The randomization procedure will follow similar procedures to those established for our ongoing pragmatic trial (IRB00307430). • Randomization must be complete by 34-weeks gestation.

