9. DATA COLLECTION AND MEASUREMENTS

9.1. Overview of measures, instrument and data sources

Table 3 summarizes the measures (with references to the standard instruments) we will use and the timing of data collection aimed at minimizing participant burden. Data will be collected using 4 methods: online surveys, home scale, medical record review, and Medicaid claims data.

Measures and Instruments	Data source(s)	Timing				
		BL	36-38wk	2 mo	4 mo	6 mo
Demographics, preferred language, acculturation, & medical history ^{58,59}	Online (+ phone assisted) surveys	x				
Discrimination experiences ⁶⁰	Online (+ phone assisted) surveys	x				
Postpartum weight retention (PPWR)	Pre-pregnancy height & weight (prior to 15 wks) from medical records	x				
Gestational weight gain (GWG)	37-weeks & postpartum weights from home scale		x	x	x	x
Safety net services & home visiting care utilization and experiences	Online (+ phone assisted) surveys	x	x	x	x	x
Maternal health care utilization	Claims + Online (+ phone assisted) surveys		x	x	x	x
Health behaviors (diet ^{61,62} ; physical activity ⁶³ ; alcohol, marijuana, tobacco use ⁵⁸ ; breastfeeding ⁶⁴)	Online (+ phone assisted) surveys	x	x	x	x	x
Maternal wellness (depression ⁶⁵ , stress ⁶⁶ , sleep ⁶⁷ , social supports ⁶⁸)	Online (+ phone assisted) surveys	x	x	x	x	x
Infant weight and length (birth weight and 2, 4, and 6 months weights)	Online (+ phone assisted) surveys & medical records			x	x	x
Infant health care utilization	Claims + Online (+ phone assisted) surveys			x	x	x

Abbreviations: BL=baseline; mo=months postpartum; wk=weeks gestation.

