15.3. Secondary outcomes and additional analyses

Analyses for between group differences in GWG and infant weights will be assessed using the same mixed-effects modeling approach with separate models similar to the main model described above. Between group differences in binary outcomes of diet, physical activity, breastfeeding and women's wellness outcomes (depression, sleep, stress, social support) will be described between H42-HV intervention and Control arms using standard cut points for the

scales and modeled using logistic regression model based longitudinal models implemented through generalized estimation equations (GEE) approach employing group indicator, visit indicators, group by visit interaction terms and adjusting for the variable used to stratified the randomization. Robust variance estimate will be used for statistical inferences to derive 95% confidence intervals for the population-average based estimates and corresponding p-values. Conforming to recommended maternal postpartum care utilization and well-baby care utilization over time will separately be modelled using similar GEE approach as described above for the longitudinal binary outcomes.

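### Gestational weight gain is a valid total-gain outcome, but its analysis leaves out the home-scale weight required before randomisation and so gives up precision, most of all for late entrants

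*Combined protocol and SAP*

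**What the plan says.** Section 15.1 gives the outcome as "GWG (37 week minus baseline pregnancy [≤ 15 week gestation] weight); Proportion with excessive GWG". Section 14.2 uses the same early anchor. It refers to 37 weeks postpartum, which I read as a slip for 37 weeks of gestation, since Section 15.1 and the late-pregnancy visit in Table 3 point that way. Section 9.2 (Medical record review) says the baseline "weight will be defined as the earliest measured weight in prenatal care obtained from prenatal medical records".

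On entry, Section 5.2.2 states: "Participants can be enrolled as early in pregnancy as 12 weeks gestation and as late as 33 weeks gestation". Table 2, Step 4 adds: "Randomization must be complete by 34-weeks gestation". The same step schedules the randomisation visit "Once the participant has completed the baseline survey and has registered one weight on the home study scale", and Section 8.2 requires that weight to be valid.

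The weight is not mentioned again as data for analysis. For GWG and postpartum weight retention (PPWR), Table 3 lists the medical-record weight and "37-weeks & postpartum weights from home scale". Section 9.2 (Home Scale) schedules "Maternal weights (measured at 37-weeks, 2 months, 4 months, and 6 months postpartum". Section 15.3 says: "Analyses for between group differences in GWG and infant weights will be assessed using the same mixed-effects modeling approach". That approach, set out in Section 15.2, treats baseline weight as one of the repeated responses. It takes the effect from the group-by-visit term and adjusts for site, BMI category and gestation at enrolment as fixed effects, with no stated interaction of these with visit.

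**The concern.** Coaching cannot change weight gained before assignment. For a late entrant that is most of what GWG counts, so the outcome carries between-woman variation that the trial could explain with a measurement it already holds. Gestation at enrolment says when a woman joined. It does not say whether she had gained little or much by then, and women who join in the same week will differ on that.

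For the proportion with excessive gain, a woman already above the recommended total at randomisation is likely to count as an event in either arm. If there are many such women, the contrast between arms is small whatever coaching achieves later. A null GWG result would then be hard to read: the coaching may not have worked, or too much of the gain may have preceded it.

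**Working it through.** **The plan's own figures.** Section 16 and Table 6 cover PPWR only. They reproduce: (1.960 + 1.282) × 5.5 × √(2/126) = 2.25 kg by the normal approximation and 2.26 kg by noncentral t, against 2.26 kg stated. No SD, effect size or power is given for GWG, so there is no GWG figure to reproduce.

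**Share of counted gain before assignment.** Inputs: record weight at 15 weeks (the latest allowed), final weight at 37 weeks, randomisation at week g. Assumption: linear gain. Share = (g − 15)/(37 − 15).

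- g = 20: 5/22 = 23%
- g = 24: 9/22 = 41%
- g = 28: 13/22 = 59%
- g = 33: 18/22 = 82%
- g = 34: 19/22 = 86%

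If randomisation were uniform over 12 to 34 weeks, with zero share up to week 15, the average is (19²/2)/(22 × 22) = 180.5/484 = 37%. The documents do not give the actual distribution.

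**Bias.** Write GWG = A + B, with A the gain before randomisation and B the gain after it. Randomisation makes the expectation of A equal in the two arms, so the expected difference in GWG is the expected difference in B. The mean contrast is unbiased, and its expected size in kg does not depend on which pre-randomisation weight is subtracted. A contributes variance.

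**Precision.** Let r be the partial correlation between GWG and gain up to the pre-randomisation scale weight, given the planned covariates. Adjustment multiplies the standard error by √(1 − r²). A comparison that had 80% power would then have power Φ(2.802/√(1 − r²) − 1.960).

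| r (assumed) | SE factor | SE cut | Sample-size equivalent 1/(1 − r²) | Power, from 80% |
|---|---|---|---|---|
| 0.3 | 0.954 | 5% | 1.10 | 84% |
| 0.5 | 0.866 | 13% | 1.33 | 90% |
| 0.7 | 0.714 | 29% | 1.96 | 97% |

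A simulation illustrates the mechanism. It assumed randomisation uniform over 15 to 34 weeks, mean gain 0.45 kg/week with SD 0.2 to 0.3 kg/week, correlation 0 to 0.6 between gain rates before and after randomisation, error SD 0.7 kg for the clinic weight and 0.5 kg for the scale, and an effect of 0.1 kg/week. Adding the early weight and the pre-randomisation scale weight left the estimated difference at about −1.25 kg. Residual variance fell to 43–61% of its value without them, that is, SE factors of √0.43 = 0.66 to √0.61 = 0.78. Those inputs are not from the trial.

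**How the covariate must enter.** In the Section 15.2 form with two occasions, suppose covariate X has the same coefficient b at both. Then E(Y₀) contains bX, E(Y₃₇) contains bX, and the change D = Y₃₇ − Y₀ contains no X. With unstructured covariance and complete data, the likelihood splits into D given group, and Y₀ given D, group and X. The group effect on D is estimated from the first part alone, so X cannot sharpen it. A simulated check (252 women, baseline and 37 weeks, complete data, assumed inputs) agrees: SE 0.614 without covariates, 0.614 with gain, gestational age and their product as main effects, and 0.448 with these crossed with visit. The same algebra applies to gestation at enrolment as written: a main effect adjusts the level of weight, not the change.

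**The case against.** The strongest reply is that this is an efficiency choice on a secondary outcome, not an error. Much of that stands. Randomisation is stratified by gestational age at enrolment, the mean contrast is unbiased, and the plan makes no power claim for GWG. Total gain has to start early in pregnancy if it is to be set against recommended total gain, which Section 14.2 uses as the comparator and Table 4 as the goal.

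A reader might infer more than the documents support:

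- **That the early anchor is wrong, or the GWG comparison biased.** Neither follows. The anchor suits the outcome, and pre-assignment gain is balanced in expectation.
- **That the excessive-gain contrast is biased towards zero.** A smaller risk difference in a group with many late entrants is the actual effect of offering the programme to the women enrolled, which is the intention-to-treat question. How many women would already exceed the limit at randomisation is unknown, so the dilution cannot be sized.
- **That the standard error would fall by a third or more.** Cuts of that size come from simulations with assumed slope variation and entry times, and different assumptions give different answers.
- **That the primary PPWR model needs the same covariate.** No benefit for PPWR has been shown.
- **That the weight is taken immediately before assignment.** Table 2 sets no maximum interval between the weight and the randomisation visit.

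What the reply does not answer is why a relevant pre-randomisation measurement, already required from every randomised woman, should be left out of the analysis.

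**Conclusion.** The point holds as a loss of precision in the GWG comparison that costs little to remove. The textual facts are clear: the early anchor, randomisation up to 34 weeks, and a required pre-randomisation scale weight that appears in no outcome list or model. The consequence is less certain. The shares of 41% at 24 weeks and 82% at 33 weeks rest on linear gain and a 15-week record weight. The standard-error cuts of about 5%, 13% and 29% rest on assumed partial correlations of 0.3, 0.5 and 0.7. The real figures depend on when women enter and how much their gain varies, and the documents give neither. The change is worth making before unblinding, so that the adjustment is not chosen after the results are seen. It does not affect the validity of the trial or its primary analysis.

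**What to change.** Keep the GWG definition and the entry window.

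1. In Table 3 and Section 9.2 (Home Scale), list the pre-randomisation home-scale weight, with the gestational age at which it was taken, as a baseline measure.
2. In Section 15.3, adjust the GWG analysis for gain from the record weight to that weight, gestational age at that weight, and their product. If the Section 15.2 type of mixed model is used, cross each term with visit. Otherwise, analyse GWG by ANCOVA with these as covariates.
3. Name the model for the proportion with excessive gain, which the list of binary outcomes in Section 15.3 does not mention, and adjust it for the same variables. As a supporting analysis, report the proportion by arm among women not already above the recommended total at randomisation. That subset is defined by pre-randomisation data, so the comparison within it remains randomised.

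The cost is protocol and analysis-plan wording, recording a date for a weight already required, and three covariate terms (with visit interactions in the mixed model). The one downside is that the supporting analysis uses fewer women.

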16.0. Sample Size and Power Estimates informing Primary Aim

We request approval for enrollment up to 400 participants with the goal of N=360 for power calculations.

Table 6. MDD for PPWR for sample of 360 with 90% power, after 30% random attrition

Power	SD of PPWR (Kg)	Minimum Detectable Difference (MDD) (Kg)
90%	5.5	2.26
90%	7.0	2.87
90%	8.0	3.28
90%	8.8	3.61

With this sample size, our objective is to determine the minimum detectable difference (MDD) for the primary outcome of PPWR between the 2 study groups. Our assumptions are as follows: Two-sided type I α error=0.05; type II β error=0.10; and 70% or greater follow-up for the main outcome of PPWR at 6-months. Based on our past experience and review of the literature, we anticipate <30% loss to follow-up for 6-month weights, consequential to drop-out of various kinds (e.g., lost to follow-up, censored due to new pregnancy). With this dropout rate and the assumption that the dropout is consistent with missing at random,

we expect to retain an effective sample size of 252 participants for our primary outcome, by randomizing N=360 participants, with 126 participants in each arm. Standard deviations for the MDD evaluation were informed by previous studies of similar combined diet-physical activity behavioral interventions to limit weight gain in pregnancy and promote postpartum weight loss^{88,89,90,91}. The MDDs range from 2.3- 3.6 kg with the assumption of 30% random attrition of the proposed sample size of 360. Based on these prior studies effect sizes we believe our sample size calculation in **Table 6** is conservative.

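### The primary model leaves the baseline group difference free, so PPWR is in effect compared as an unadjusted change score; a common baseline mean and the pre-randomisation home-scale weight would add precision at no cost in data

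*Combined protocol and SAP*

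**What the plan says.** Section 14.1 (definition of the primary outcome) makes PPWR the difference between a prenatal-record weight at 15 weeks or earlier and the 6-month home-scale weight. Section 15.2 models the longitudinal weights with baseline as the reference visit. The mean model has "a group indicator (0 for Group B and 1 for Group A), 3 visit indicators for 2, 4, and 6 months respectively", plus group-by-visit terms. Site, BMI category and gestation at enrolment enter as fixed effects, with no interaction with visit described. The covariance is unstructured. The effect is defined thus: "The regression coefficient of the group by 6-months postpartum weight interaction term will estimate the primary outcome". Nothing sets the baseline means of the two arms equal, and continuous baseline weight is not a covariate.

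A second weight is taken before assignment. Table 2 in section 8.1 schedules the randomisation visit "Once the participant has completed the baseline survey and has registered one weight on the home study scale", and section 8.2 (Step 4) requires one valid scale weight first. Section 15.2 does not use it.

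Section 16.0 plans with "Two-sided type I α error=0.05" and "type II β error=0.10". Table 6 works from the SD of PPWR itself, which is the SD of a change score.

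**The concern.** Because the group main effect is free, the model estimates a baseline difference between arms that randomisation makes zero in expectation, and subtracts that estimate from the 6-month difference. The sampling error in the baseline difference then stays in the treatment effect.

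The home-scale weight carries information of a different kind. Women join between 12 and 33 weeks (section 5.2.2), so this weight records gain that the intervention cannot have caused and that may predict retention at 6 months. Adjusting for it leaves the estimand unchanged.

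At stake is precision on the primary outcome, in a trial that allows for up to 30% loss of 6-month weights.

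**Working it through.** **1. Reproduce Table 6.** Inputs from section 16.0: two-sided alpha 0.05, power 90%, 360 randomised, 30% loss, so 360 × 0.70 = 252 analysed, 126 per arm.

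Normal approximation: MDD = (1.960 + 1.282) × SD × √(2/126) = 0.408 × SD. The noncentral t distribution gives slightly more.

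| SD of PPWR (kg) | Normal | Noncentral t | Table 6 |
|---|---|---|---|
| 5.5 | 2.246 | 2.255 | 2.26 |
| 7.0 | 2.859 | 2.870 | 2.87 |
| 8.0 | 3.267 | 3.280 | 3.28 |
| 8.8 | 3.594 | 3.608 | 3.61 |

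Table 6 is therefore an unadjusted two-sample comparison of mean change, with no allowance for baseline adjustment. It agrees with the model in section 15.2.

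**2. What the planned coefficient estimates.** A covariate whose effect is the same at every visit cancels when baseline is subtracted. In one simulated complete dataset of 252 women, with BMI category and eight sites as main effects and a chance baseline difference of 1.25 kg:

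- planned group-by-6-month term: -1.27042 (SE 0.881)
- raw difference in mean change: -1.27042
- model with a common baseline mean: -1.28864 (SE 0.873)

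In a separate calculation from the information matrix, the SE of the planned term was 0.6929 both with and without BMI category.

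**3. Gain from a common baseline mean.** With complete data, variance ratio (constrained to planned) = 1 − c², where c is the correlation of change with baseline weight. The documents do not give c, so two cases bound the range used here.

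- *Equal variances at baseline and 6 months.* Then rho = 1 − SDchange²/(2 × SDbase²) and the ratio is (1 + rho)/2. At PPWR SD 7 and weight SD 18: rho = 1 − 49/648 = 0.924, ratio 0.962, MDD 2.87 × √0.962 = 2.82 kg, worth about 10 of the 252 analysed women. Over weight SD 15-20 kg (assumed) and the SDs in Table 6, the ratio runs from 0.914 (15 and 8.8 kg) to 0.981 (20 and 5.5 kg), so the MDD falls by about 1% to 4%.
- *Change uncorrelated with baseline weight.* Then c = 0 and the gain is zero. This needs a 6-month SD of √(SDbase² + SDchange²), for example √(324 + 49) = 19.3 kg against 18 kg at baseline.

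**4. Missing 6-month weights.** If the 30% lost have only a baseline weight, the likelihood uses it a little: the planned model's variance is 0.4% to 4% below that of the completers' raw change (weight SD 12-25 kg, equal variances). The constraint still helps: at weight SD 15 and 18 kg, and PPWR SD 5.5 and 8.8 kg, the ratio is 0.94 to 0.98.

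**5. Adding the home-scale weight (illustration only).** If it has correlation r with 6-month weight given baseline weight, the variance is multiplied again by 1 − r². At PPWR SD 7 and weight SD 18, equal variances:

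| r (assumed) | Variance ratio to plan | MDD (kg) |
|---|---|---|
| 0 | 0.962 | 2.82 |
| 0.20 | 0.962 × 0.96 = 0.924 | 2.76 |
| 0.30 | 0.962 × 0.91 = 0.876 | 2.69 |

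**The case against.** The strongest reply is that nothing here is incorrect. The outcome is defined as a change, the model estimates the difference in mean change, the estimator is unbiased under randomisation, and the sample size matches it. A longitudinal model with a free baseline is a common choice. All of that stands.

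Several stronger readings are tempting, and the documents do not support them:

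- *That chance baseline imbalance biases the result.* It is sampling error, already inside the standard error, and stratification by BMI category (section 11) limits it. At PPWR SD 7 and weight SD 18, an imbalance of one standard error, 18 × √(2/126) = 2.27 kg, shifts the estimate by (1 − 0.924) × 2.27, or about 0.17 kg.
- *That baseline weight is never used.* This is exact only for complete data; see step 4.
- *That a large gain has been shown.* The baseline-only gain is small and can be zero. Anything beyond it rests on a correlation that no section reports, and enrolment from 12 to 33 weeks means that gain up to the weighing covers very different lengths of pregnancy.
- *That baseline weight could equally be moved to the covariates.* It comes from prenatal records, mostly requested from outside providers (section 9.2), and must date from 15 weeks or earlier, so some may be missing. A covariate model would drop those women unless their values were imputed, whereas section 15.2 intends to use everyone randomised.

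One counter-argument fails: adjusting for BMI category does not already do the job, as step 2 shows.

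**Conclusion.** The point holds as a modest matter of efficiency. With complete data the planned primary contrast is an unadjusted change score, and two weights known before assignment add nothing to its precision beyond the subtraction of baseline. Validity is not in question and Table 6 needs no correction.

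For an assumed weight SD of 15-20 kg, the common-baseline constraint is worth 0% to about 4% of the MDD. The upper end requires equal variances at the two times. Whether the home-scale weight adds anything cannot be settled from the documents. If it adds nothing, little is lost: in simulation with r = 0, the variance ratio was 0.965 with it and 0.962 without it. The case for changing the plan is that the improvement is free, not that it is large.

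**What to change.** In section 15.2:

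1. Remove the group main effect so that both arms share one baseline mean. Keep baseline weight in the response vector, with the visit and group-by-visit terms and the unstructured covariance. Women without a usable record weight then stay in the analysis.
2. Prespecify the pre-randomisation home-scale weight, and gestational age at that weighing, as covariates crossed with visit.
3. State that the group-by-6-month coefficient remains the primary estimate.

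The estimand, data collection and sample size do not change, and Table 6 can stand as slightly conservative. The cost is SAP wording and a few degrees of freedom. The change should be dated before any outcome data are seen by arm, because covariates added later would look chosen from the results.
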